9 ADVERSE EVENTS

9.1 Definitions

9.1.1 Adverse Event

Any untoward medical occurrence in a subject, who has received IMP, will be registered. The occurrence does not necessary have to have a causal relationship with the IMP. An AE can therefore be any unfavourable and unintended sign (e.g. an abnormal laboratory finding), symptom, or disease temporally associated with the use of an IMP, weather or not considered related to the IMP.

9.1.2 Serious Adverse Event

An SAE is any untoward medical occurrence or event, at any dose, that:

- Results in death
- Is life threatening
- Requires hospitalisation or prolongation of existing hospitalisation
- Results in persistent or significant disability/incapacity
- Is a congenital anomaly/birth defects.

Or

• Other important medical event (example of such events are convulsions that do not result in hospitalisation)

Medical and scientific judgment should be exercised in deciding whether expedited reporting is appropriate in other situations, such as important medical events that may not be immediately life-threatening or result in death or hospitalisation but may jeopardise the subject's health or may require intervention to prevent one of the other outcomes listed in the definitions above. These AEs should also usually be considered as *serious*.

9.1.3 Suspected Unexpected Serious Adverse Reaction (SUSAR)

A SUSAR is a suspected unexpected serious adverse reaction, potentially causally related to the investigational medicinal product, and will be reported to the appropriate IEC and Regulatory Authorities. A Serious Adverse Reaction is expected if it is mentioned in the Summary of Product Characteristics (SPC) for Tamoxifen Mylan.

9.2 Reporting of SUSARs

Only SAEs that are both unexpected and assessed as related to IMP(s), i.e. SUSARs, are subject to expedited reporting by the Sponsor to the appropriate IEC and Regulatory Authorities, as per local requirements.

The sponsor must report all SUSARs that resulted in death or was life threatening to the authority and to the IEC within 7 days, and if necessary complete the follow up report within the following 8 days. Other SUSAR should be reported within 15 days.

9.3 Eliciting and recording of AEs

The method for collecting and recording AEs will be through the web-based questionnaire each study participant has to fill in at a regular basis during the study period. Additionally, the participants can at any time report AEs to Karma Staff by contacting Karma Study Centre. All AEs, serious and non-serious, will be recorded in the eCRFs. If no AE has occurred during the study period, this should also be recorded.

9.4 AEs of interest

In the questionnaire (Appendix 14.2) are AE:s of interest listed.

In the questionnaire it's also possible to address not stated adverse events by writing free text. These answers are continuously monitored by Karma staff in order to take immediate action if there are any signs of adverse events of interest or possible serious adverse event. Potential serious adverse events are signs of thromboembolism or gynaecological bleedings.

An alarm system in the e-CRF will alert personnel at the Karma Study Centre when an AE of interest is recorded so evaluation and follow up can be performed throughout the study period.

All AEs of interest will be coded according to Medical Dictionary for Regulatory Activities - MedDRA. The Investigator will perform the coding.

The following evaluations are to be done by the Investigator in connection with the AE of interest:

- Description of the AE. If possible the investigator uses the diagnosis for description of the event. If no diagnosis is decided, each symptom will be described.
- Seriousness
- Yes or No, see definition of a SAE for seriousness, as of above.

- Intensity (if the intensity changes during the period of the AE the maximum intensity should be recorded)
- Mild symptoms which are easily tolerated (acceptable)
- Moderate symptoms which interfere with usual activity (disturbing)
- Severe symptoms which give incapacity to do usual activity (unacceptable)
- Duration of the AE (start end)
- Action taken due to the AE
- None
- IMP stopped
- Additional details on action taken, including diagnostic procedures, will be recorded for any women with vaginal bleeding or discharge. Any women who report abnormal vaginal bleeding or discharge or pelvic pain or pressure, should be promptly investigated. It is not mandatory that the study code is broken in such cases, but this may be done if requested by the treating physician, necessary for further treatment.
- Causality rating with investigational medicinal product
- Not related: Indicates that the AE is definitely not related to the study drug.
- Unlikely: The adverse onset and the medicinal product administration is such that the medicinal product is not likely to have any reasonable association to the AE.
- Possible: The subject's clinical status or the medicinal product could have produced the AE.
- Probable: The AE follows a reasonable temporal sequence from the time of administration of the medicinal product, abates upon discontinuation of the medicinal product and cannot be reasonably explained by the known characteristics of the subject's clinical status.
- Not assessable: There is not sufficient information to assess causality between the medicinal product and the suspected reaction.
- Outcome of the AE
- Recovered/Resolved
- Recovering/Resolving
- Not recovered/Not resolved
- Recovered/Resolved with sequelae
- Fatal
- Unknown

9.5 Reporting of SAEs

It is important to distinguish between serious and severe adverse events. Severity is a measure of intensity whereas seriousness is defined by the criteria in the previous sections. An adverse event of severe intensity need not necessarily be considered serious. For example nausea, which persists for several hours, may be considered severe nausea but not a serious adverse event. On the other hand, a stroke resulting only in limited degree in disability may be considered a mild stroke but would be considered a serious adverse event.

All SAEs must be reported by the Investigator using phone or fax within 24 hours from the Investigator's knowledge of the event to the Sponsor regardless of the time that may have elapsed from the time the event occurred to when the Investigator first learns of it. The initial report should contain as a minimum the following information:

- Subject identification
- Treatment specification
- Diagnosis or symptoms
- Name of the original reporter

A SAE report form must also be completed, signed by the Investigator and submitted to the sponsor no later than five working days after the initial information was received. Apart from the information above, this follow-up report should also contain the following information:

- Assessment of intensity
- Assessment of causality

9.5.1 Follow-up of unresolved AEs

If a subject is withdrawn due to an AE, or if an AE persists at the end of the study treatment period, this should be followed up until the condition has ceased or until the subject is under professional medical care and a potential causality between IMP and the AE has been penetrated. An outcome assessment should be performed when an AE persists.

9.5.2 Procedures in case of pregnancy

In case of pregnancy or suspicion of possible pregnancy, the study treatment must be stopped immediately, and the subject discontinued from participation in the study. Pregnancy itself is not regarded as an AE unless there is a suspicion that the IMP may have interfered with the effectiveness of the contraceptive medication. However, the outcome of all pregnancies (e.g. spontaneous miscarriage, elective termination, normal birth or congenital abnormality) must be followed up and documented even after the subject was discontinued from the study.

All events of congenital abnormalities/birth defects are SAEs. Spontaneous miscarriages should also be reported and handled as SAEs. All outcomes of pregnancy must be reported to Karma Study Centre.

10 DATA QUALITY ASSURANCE

10.1 Electronic Case Report Forms (eCRFs)

The site personnel will enter the information required for the study in the eCRF. Data will also be imported from web questionnaire, medical records and laboratory findings.

10.2 Monitoring

The Karisma II study will be monitored according to ICH-GCP guidelines, Regulatory requirements and the study specific Monitoring plan. The Karisma II study will be monitored by an independent Monitor according to ICH GCP Guidelines. Study conductance, source data and adherence to the study protocol will be monitored. The Investigator's duty is to inform all personnel concerned about the trial and, if necessary, educate and train all persons participating in the study. This should be checked by the monitor.

10.3 Source data

Source data will be handled according to regulatory requirements. A source data location list will be kept at the investigational site for definition of source data.

10.4 Audit and inspections

The study site may be subject to quality assurance audit by the Sponsor or someone appointed for this task by the Sponsor. A Regulatory Authority may request to make an inspection of the study site. The procedures of such a visit would be similar to those of a monitoring visit, and data already checked by the Monitor may be checked again. The Investigator is required to inform Karisma II study immediately of an inspection requested by a Regulatory Authority. The investigator and other relevant personnel must be available during the audit/inspection and must devote sufficient time.

10.5 Changes in the approved Study Protocol

Study procedures must not be changed without the mutual agreement of the Investigator and Sponsor.

Any substantial change to the approved Final Study Protocol will be documented in a written and numbered Protocol Amendment. Any proposed substantial change to the Final Study Protocol must be discussed with and approved by Sponsor/Investigator before submitted to IEC and Regulatory Authority for approval, according to applicable national regulations.

10.6 Statistical methods and determination of sample size

All analyses will be performed after the study is completed and the database is released. All statistics, including tables, figures and listings, will be performed using SAS®, Version 9.3, and R, Version 3.x.

The statistical analysis are described in detail in the Statistical Analysis Plan (SAP) including a Data Display Plan (DDP), which will be in a final draft version prior to study start and finalised and approved before database lock.

10.6.1 Demographics and baseline data

All data will be presented using descriptive statistics. Results will be presented in total, by treatment group, age and as menopausal status. Continuous variables will be summarised using number of women, mean, standard deviation, median, minimum and maximum. Categorical variables will be summarised using the number and percentage of women.

10.6.2 Analysis of the primary endpoint (effectiveness)

The primary analysis will be performed on an intention to treat (ITT) basis.

The results of both papers [4] and [5] showed that a threshold value in mammographic density decrease needs to be exceeded in order for a woman to experience the beneficial effect of tamoxifen. This threshold value was different in [4] compared to [5]. A 10% or greater reduction was needed in [4] whereas a 20% reduction was needed in [5], a difference most likely explained by different methods of measuring mammographic density. However, the proportion of women exceeding this threshold was exactly 48% in both studies, implying that approximately 50% of the women experience the beneficial effect of tamoxifen irrespective of the way mammographic density is measured.

In the Karma II study, we will use area based mammographic density, which was used in both [4] or [5]. With support of the results in [4] and [5], we define the *response threshold* to be the *median decrease* in mammographic density of women in the 20 mg tamoxifen arm (this definition ensures that the same proportion of women exceeds the threshold as observed in

previous studies). Further, we define a *responder* to be a woman whose mammographic density decrease between baseline and 6 months exceeds the response threshold.

Compliance of study drug intake is defined as at least 80% of the prescribed numbers of tablets should be used during time of treatment (i.e. 6 months).

The primary efficacy endpoint is the *proportion of responders* (women with a reduction of mammographic density, from baseline to 6 months). We will test for non-inferiority with respect to the primary efficacy endpoint for groups of women treated with placebo, 1, 2.5, 5, and 10 mg compared to the group of women treated with 20 mg tamoxifen. The non-inferiority margin is defined to be 16.7 percentage points; that is, we define non-inferiority to mean that the fraction of responders is not less than one third of the treated individuals (50% minus 16.7% = 33.3%).

The null hypothesis is thus that the proportion of responders in women treated with placebo, 1, 2.5, 5, and 10 mg is 16.7 percentage points less than those women treated with 20 mg tamoxifen (i.e. the fraction of responders is less than one third).

We will also perform sensitivity analyses where the threshold is varied ± 10 percentage points.

10.6.3 Sample size

With 168 patients in each treatment group, the lower limit of the observed one-sided 98.5% confidence limit for the difference will be expected to exceed the non-inferiority margin 16.7 percentage points with a 80% power, assuming that the expected difference in responders between two arms is 0 and the proportion responders in the 20 mg tamoxifen group is 50%. With an estimated 30% drop-out rate, 240 patients in each group need to be randomized. The computations are based on the following formula:

$$n = f(\alpha, \beta) \times [\pi_s \times (100 - \pi_s) + \pi_e \times (100 - \pi_e)] / (\pi_s - \pi_e - d)^2$$

where π_s and π_e are the true percent 'success' in the standard (20mg) and experimental treatment group respectively, and

$$f(\alpha, \beta) = [\Phi^{-1}(\alpha) + \Phi^{-1}(\beta)]^2$$

 Φ^{-1} is the cumulative distribution function of a standardised normal deviate.

10.6.4 Analysis of the secondary outcome

We will assess the proportion of drop-outs at six months and test for differences in the proportion of drop-outs in the intervention arms compared with the 20 mg arm. We will use Fisher's exact test with an p-value of less than 0.05 (corrected for multiple testing, see SAP Section 6.7) as a threshold to declare statistical significance.

10.6.5 Analysis of tertiary outcomes

Tertiary outcomes will be analysed with statistical methods appropriate for the specific outcome. For example, the association of plasma concentrations of endoxifen with responder status will be analysed with logistic regression both within treatment groups and among treatments groups (treatment group will be handeled as a random effect in the latter case). Full details of the analysis of tertiary outcomes will be in the statistical analysis plan (SAP) prior to database release.

10.6.6 Examination of subgroups

We will perform subgroup analyses, where the subgroups are CYP2D6 polymorphism status

(excellent, intermediate, poor metaboliser). CYP2D6 polymorphism status will be handled as a categorical fixed effect variable.

10.6.7 Interim analysis

We will three months into the study perform an interim analysis on overall dropout level. If the proportion of drop out at three months, we will – at best – have 73% power for our primary analysis (see SAP Section 6.6). In this case, we will increase the number of women the study needs to accrue according to:

$$n_{tot} = 168 \times 6/(1-d)$$
,

where d is the overall proportion of drop outs at three months.

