Karisma II: A randomized, double blinded, six-armed placebo controlled study to investigate optimal dose of tamoxifen with the most favourable side effect spectra and with mammographic density reduction non-inferior to that of 20 mg tamoxifen.

Substance: Tamoxifen

EudraCT: 2016-000882-22

Coordinating Investigator, Principal

Investigator and Sponsor:

[name], Professor
Karolinska Institutet

Institution for Medical Epidemiology and Biostatistics

[name] [contact] Email: [contact]

PROTOCOL REVISION HISTORY

Version	Date	Revised by	Description of change	Refers to
				chapter/page
1.0	2016-04-21	NA	Initial version.	NA
2.0	2016-06-29	NA	Revised after feedback from MPA. For details see reply to MPA dated 1 July 2016	NA
2.1	2017-01-02		Revised after inclusion in Lund 20161114- 1202 and before recruitment in Sthlm	

PROTOCOL SYNOPSIS

Study Title

Karisma II: A randomized, double blinded, six armed, placebo controlled study to investigate optimal dose of tamoxifen with the most favourable side effect spectra and with mammographic density reduction non-inferior to that of 20 mg tamoxifen.

Study code KARISMA II

EudraCT No: 2016-000882-22

Coordinating Investigator

[name]

Study centre(s) -

Karma Study Centre / Breast and Mammography screening unit, Södersjukhuset, Stockholm, Sweden

Karma Study Centre / Unilabs mammography unit / Klinska prövningsenheten, Skånes Universitetssjukhus i Lund, Lund, Sweden

Study period Phase of development Estimated date of first subject enrolled, November 2016 Estimated date of last subject completed, December 2017 Phase of development Phase II

Objectives and endpoints

Primary objective: Identify the minimal dose of tamoxifen non-inferior in its ability to reduce mammographic density compared to 20 mg of tamoxifen

Primary endpoint: Change in mammographic density and levels of side effects after 6 months. In particular, we will test for noninferiority in the proportion of women in the intervention arms (placebo, 1 mg, 2.5 mg, 5 mg, 10 mg) who have a density reduction as great as or greater (after 6 months) than the median density reduction in the 20 mg arm

Secondary objectives: Assess the drop-out level and the level of side effects in the intervention arms compared to the 20 mg arm.

Secondary endpoints: Drop-out rate. We will test for differences in the proportion of drop-outs after 6 months in the intervention arms compared to the 20 mg arm.

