Tertiary objectives: Relate levels of tamoxifen metabolites, proteins, lipids and hormones in blood and changes in breast tissue to different tamoxifen doses. Measure genetic polymorphism in germline DNA and relate it to the other tertiary objectives. Measure mammographic density and levels of side effects 6 months after tamoxifen cessation in relation to treatment arm

Tertiary endpoints: Levels of tamoxifen metabolites, proteins, lipids and hormones in blood. Breast tissue changes. Genetic polymorphism in germline DNA. Mammographic density and levels of side effects 6 months after tamoxifen cessation

Study design

Randomized, double blinded, six-armed, placebo controlled clinical trial

Number of subjects planned

1,440

Diagnosis and main eligibility criteria

Healthy women participating in mammographic screening with a a measurable mammographic density, i.e. ≥4.5 % density (volumetric) measured by Volpara.

Investigational Medical Product

Investigational product - Tamoxifen

Dosage – 20 mg, 10 mg, 5mg, 2.5 mg, 1 mg and 0 mg (placebo)

Oral administration, one tablet once daily

Duration of treatment

6 months

Duration of subjects involvement in the study

6 months for the SÖS-cohort (1400 particip), 12 months for the Lund cohort (40 paticip)

Efficacy assessments

Mammographic density after 6 months

Plasma levels of tamoxifen metabolites, proteins, lipids and hormones in blood

Genetic polymorphism measured in germline DNA

Safety assessments

Monitoring and recording of all AEs and SAEs

Statistical methods

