5.4 Study length and study period

There are three studies [4,5,6] that used mammographic density change during one year as a proxy for tamoxifen effect. Two projects studied the association between mammographic density change in patients and prognosis and one study looked at density change among perfectly healthy woman and risk of breast cancer. All three studies came to the same result, approximately half of the treated participants respond to the therapy by a significant reduction in mammographic density after one year. Those that respond with a decreased mammographic density had a lower risk of breast cancer recurrence and a lower risk of breast cancer.

The main reason we conducted the Karisma I study was to investigate time to density change. Radiologists tell us that the time to density change is most probably much shorter than one year, probably only a couple of months. However, the issue of time to density change during tamoxifen therapy has never been addressed.

The results from Karisma I show that, regardless of dose, density decreases within 6 months by about 50% for one quarter of the participants, about 20% for another quarter and not at all for the other participants. This result implicates that tamoxifen intake during 6 months gives a measurable density change of responders; therefore, the treatment period in Karisma II are set to 6 months.

From a clinical point of view and for coming study (Karisma III) we will investigate the state of density change and decline of side effects 6 months after tamoxifen cessation in relation to doses. This will be done exploratory and only for the Lund-cohort.

The study period will be at least 14 months since we plan to run Karisma II at two sites successively:

Site	Karma Study Centre Lund	Karma Study Centre Stockholm/SöS					
Number of participants	Approximately 40	Approximately 1400					
First enrolment	November 2016	February 2017					
End of treatment	May 2017	December 2017					
End of follow	November 2017	December 2017					

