11 STUDY MANAGEMENT

11.1 Study time table - End of study

The study is planned in two steps geographically (see 5.4). The first inclusion phase will start in November 2016 in Lund. Last participant in Lund will end medication in May 2017 and will do the final examinations in November 2017. In the overlapping second phase we will start inclusion at Södersjukhuset, Stockholm, by November 2016 and end the study by May 2018.

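### The drop-out interim has no minimum number of women, and taken literally it falls when only about 40 Lund women can have three months of follow-up

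*Protocol*

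**What the plan says.** Protocol 10.6.7 and SAP 6.8 use the same sentence: "We will three months into the study perform an interim analysis on overall dropout level". If drop-out is high enough that power is at best 73%, the total is raised to 168 × 6/(1 − d), "where d is the overall proportion of drop outs at three months". In the text available, the conditional sentence shows no drop-out level that would trigger the increase. Neither section gives a calendar date, a minimum number of women followed, or an allowance for the imprecision of d.

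On the timetable, Protocol 5.4 says "we plan to run Karisma II at two sites successively". Its table has about 40 women starting in Lund in November 2016 and about 1,400 starting in Stockholm in February 2017. The Protocol revision history describes version 2.1, dated 2 January 2017, as "Revised after inclusion in Lund 20161114- 1202 and before recruitment in Sthlm". Protocol 11.1 disagrees with 5.4: "we will start inclusion at Södersjukhuset, Stockholm, by November 2016 and end the study by May 2018".

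**The concern.** The interim has one purpose, which is to correct the sample size if drop-out exceeds the planned 30%. Its value therefore depends on how many women contribute to d. If the analysis is run when the wording says, the data come from one site and from under 3% of planned enrolment (40/1,440 = 2.8%). A real shortfall could then go unseen, leaving the non-inferiority comparisons underpowered. Less often, a chance excess of drop-outs would lead to several hundred more healthy women being randomised without need. Protocol 5.1 acknowledges that taking part brings participants no obvious individual advantage.

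**Working it through.** **1. The plan's own figure.** Protocol 10.6.3 starts from "With 168 patients in each treatment group, the lower limit of the observed one-sided 98.5% confidence limit for the difference", with a margin of 16.7 points, 80% power, 50% responders in both arms and 30% drop-out. The plan's formula gives n = (2.170 + 0.842)² × (0.25 + 0.25)/0.167² = 163 per arm. This is within 3% of the stated 168, and power at 168 is 81.4%. The inflation matches exactly: 168/0.70 = 240 per arm, and 168 × 6/0.70 = 1,440.

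**2. Who has follow-up at the literal date.** Lund inclusion ran from 14 November to 2 December 2016, so three months into the study is about mid-February 2017. The last Lund women reach month 3 only on about 2 March, which makes 40 an upper limit. Stockholm had not begun on 2 January 2017, so no Stockholm woman could have more than about six weeks of follow-up. The revision history therefore rules out the November 2016 Stockholm start in 11.1.

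**3. Precision of d from 40 women at 30% drop-out.**
- Standard error: √(0.30 × 0.70/40) = 7.2 points.
- Normal 95% half-width: 1.96 × 7.2 = 14.2 points.
- Exact 95% interval for 12/40: 16.6% to 46.5%, a half-width of 15.0 points.

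**4. The implied trigger (assumption).** By the plan's formula, 73% power needs 0.5 × ((2.170 + 0.613)/0.167)² = 139 evaluable women per arm. Out of 240 randomised, that is drop-out of 1 − 139/240 = 42%. This is taken as the trigger below.

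**5. How the rule performs.** A 42% trigger means at least 17 drop-outs among 40 women (0.42 × 40 = 16.8), or at least 147 among 350.

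| True drop-out | Event | 40 women | 350 women |
|---|---|---|---|
| 45% | shortfall missed | 32% | 12% |
| 30% | false trigger | 6.3% | about 1 in a million |

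At 45% drop-out, 132 women per arm are evaluable (240 × 0.55) and power is about 71%. With a 40% trigger (at least 16 of 40), the false-trigger chance at a true 30% rises to 11.5%. At the 25% discontinuation reported for the pilot in Protocol section 4, the false-trigger chances are 1.2% (42% trigger) and 2.6% (40% trigger).

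**6. Size of a false increase.** The smallest triggering result, 17/40, gives 1,008/(1 − 0.425) = 1,753 women, which is 313 more than 1,440.

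**7. Women needed for a usable estimate.** For a 5-point 95% margin at 30% drop-out: 1.96² × 0.21/0.05² = 323. With d between 25% and 35%, the formula then gives 1,344 to 1,551.

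**The case against.** The strongest reply is that the wording may refer to participant time. SAP 6.9 speaks of imputing density six months into the study for women who dropped out, which is time since each woman's entry, and Protocol 7.9 equates the treatment period with the first six months of the study. The definition of d also fits the 3-month questionnaire. This stands as a possible reading, so a reader should not infer that the interim must run on 40 women. The calendar reading is still the natural one for a sentence about when an analysis is performed. The other reading defines what d measures, but leaves open when the data are cut and how many women contribute.

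A reader might also carry the exact interval straight through the formula and conclude that the total could land anywhere from 1,208 to 1,885. The documents do not support the lower part of that range: the formula applies only once drop-out is too high, and the action is an increase. Nothing below 1,440 can result. Nor is large over-recruitment likely: it is about a 6% event at the planned 30% drop-out.

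Two further points stand. A better cut-off does not make the rule workable without a stated threshold. Separately, d is measured at three months while the formula is built on six-month drop-out, so d would tend to be too low however many women are followed.

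**Conclusion.** The concern holds in a limited form. The timing sentence sets no minimum number of women. On its literal reading the interim rests on at most about 40 women from one site, with a 95% margin of 14 to 15 points (standard error 7.2 points). On the participant-time reading the cut-off is undefined.

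The more likely harm is a missed shortfall: about 32% of the time at a true 45% drop-out, against about 12% with 350 women. A false increase is less likely, about 6% at a true 30%, but costs at least about 313 extra women. The margin assumes 30% drop-out among 40 women. The error rates assume independent drop-outs and a trigger near 42%, which is inferred from the 73% power figure. Type I error is not affected. The point merits correction but does not undermine the primary analysis.

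**What to change.** In Protocol 10.6.7 and SAP 6.8:
- Replace the calendar timing with a count. For example, the interim takes place when about 300 or more randomised women, including Stockholm women, have reached their 3-month assessment, and before Stockholm accrual closes. About 323 women give a 5-point margin.
- State the drop-out level that triggers the increase.

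Reconcile the Stockholm dates in Protocol 5.4 and 11.1 first, because they decide whether the cut-off falls before accrual ends.

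The text change is small, and d is a pooled proportion of drop-outs already being recorded, so no unblinding is needed. The real cost is time. Under 5.4, Stockholm treatment ends in December 2017, so six-month treatment puts the last enrolment near June 2017. If 1,400 women accrue evenly over about five months (280 a month), the 323rd woman overall (the 283rd in Stockholm) enters around early March and reaches month 3 in early June. Only a few weeks would remain to act. Under the May 2018 end in 11.1, accrual could run to about November 2017 and there would be ample room.

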7.10 Criteria for withdrawal

The Subject should be excluded from the study if, in the opinion of the Investigator, it is medically necessary, or if it is the expressed wish of the subject. Women are free to discontinue their participation in the study at any time.

Irrespective of the reason for withdrawal and whenever possible, the subject should be encouraged to return for a clinical visit at the time of or soon after discontinuation and complete

all evaluations which may be necessary to assure that the subject is free from any untoward effects and to perform appropriate follow-up for any continuing medical event. Relevant laboratory test samples should be obtained and all relevant assessments should be completed, preferably according to the scheme for the final assessment. The eCRF should be completed as far as possible.

A withdrawn subject is not allowed to re-enter into the study. The criteria for withdrawal are the following:

- A woman develops breast cancer, including ductal carcinoma in situ (DCIS).
- Subject wishes to discontinue
- Unacceptable adverse event/side effect
- Non-compliance with the study protocol
- Subject refuses to cooperate
- Other medical reasons
- Pregnancy

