## 6.8 Interim analysis

We will three months into the study perform an interim analysis on overall dropout level. If the proportion of drop out at three months, we will – at best – have 73% power for our primary analysis (under the same assumptions as described in Section 6.6, apart from the assumption about the proportion of drop outs). In this case, we will increase the number of women the study needs to accrue according to:

$$n_{tot} = 168 \times 6 / (1 - d'),$$

where  $d'$  is the overall proportion of drop outs at three months.

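### The interim rule re-sizes the trial from drop-out at three months, although the 168 women per arm are needed at six months

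*Protocol*

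**What the plan says.** The primary endpoint is density change from baseline to six months (Protocol 10.6.2, SAP 6.3). Protocol 10.6.3 asks for 168 women per arm and then inflates: "With an estimated 30% drop-out rate, 240 patients in each group need to be randomized". The secondary analysis also treats drop-out as a six-month quantity: "We will assess the proportion of drop-outs at six months and test for differences".

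The interim rule uses a different time. SAP 6.8 says: "We will three months into the study perform an interim analysis on overall dropout level". Protocol 10.6.7 continues: "If the proportion of drop out at three months, we will – at best – have 73% power for our primary analysis". The condition has no drop-out value in either document. If it is met, the total rises to 168 x 6/(1-d), "where d is the overall proportion of drop outs at three months"; the SAP likewise defines its d' as what "is the overall proportion of drop outs at three months". Neither section projects drop-out from month 3 to month 6. Protocol 7.10 adds: "A withdrawn subject is not allowed to re-enter into the study".

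On timing, the revision history has the entry "Revised after inclusion in Lund 20161114- 1202 and before recruitment in Sthlm". Protocol 5.4 gives about 40 women in Lund, and about 1,400 in Stockholm with first enrolment in February 2017.

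**The concern.** The interim formula has the same form as the original inflation, 168/(1 - drop-out), but the drop-out put into it covers only the first half of treatment. Cumulative drop-out cannot fall after month 3, because withdrawn women may not return. The re-sized trial therefore reaches 168 per arm at month 6 only if drop-out stops at month 3.

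The rule exists to protect power when drop-out is worse than planned. If it under-corrects, a non-inferiority comparison can miss a dose that truly is non-inferior to 20 mg. Power is what is at stake. The look uses pooled drop-out only, so neither type I error nor bias in the comparison is affected.

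**Working it through.** **Inputs.** One-sided alpha 0.015 (98.5% limit), margin 16.7 points, 50% responders in both arms, 168 per arm, 30% drop-out, 240 randomised per arm (Protocol 10.6.3, SAP 6.6).

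**Plan's own figure.** n = (2.170 + 0.842)² x (50x50 + 50x50)/16.7² = 162.6. The stated 168 is slightly above this. Power = Φ(√(n x 16.7²/5000) - 2.170), which at n = 168 is 81.4%. Also 168/0.70 = 240 and 6 x 240 = 1,440. The plan reproduces, with a cushion of about 5 women per arm.

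**Implied trigger.** 73% power needs n = 138.8, and 1 - 138.8/240 = 42.1%. If 168 is instead taken to give exactly 80%, n = 168 x 138.8/162.6 = 143.4 and drop-out is 40.2%. So about 40-42%; 40% is used below as an assumption.

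**Rule at d = 40%.** 168 x 6/0.60 = 1,680, or 280 per arm. Power reaches 80% at 162.6 per arm, so the break-even six-month drop-out is 1 - 162.6/280 = 41.9%, which is 1.9 points after month 3. If 168 is taken as exactly 80%, there is no cushion.

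| Drop-out after month 3 | Six-month drop-out | Left per arm (of 280) | Power |
|---|---|---|---|
| 0 points | 40% | 168 | 81.4% |
| 2 points | 42% | 162.4 | 79.9% |
| 5 points | 45% | 154 | 77.7% |
| 10 points | 50% | 140 | 73.4% |

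With 10 further points the enlarged trial is back at about the power that the rule treats as too low. The totals needed would have been 1008/0.55 = 1,833 at 45% and 1008/0.50 = 2,016 at 50%.

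**The trigger has the same gap.** The share of drop-outs that occur by month 3 is not given. If it is 90% or 80% (assumed), a 40% trigger at month 3 corresponds to six-month drop-out of 0.40/0.9 = 44.4% or 0.40/0.8 = 50%.

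**Recovery by exit mammograms.** To get back to 162.6 per arm:
- at 5 further points, (162.6 - 154)/126 = 7% of drop-outs must supply one;
- at 10 further points, (162.6 - 140)/140 = 16%.

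**Calendar reading.** Lund enrolled from 14 November to 2 December 2016. Three months after first enrolment is 14 February 2017, when those roughly 40 women have 74 to 92 days of follow-up and Stockholm is only opening. At 30% drop-out the 95% half-width is 1.96 x √(0.21/n): 14.2 points with 40 women, 6.4 with 200.

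**The case against.** The strongest reply is that a drop-out is not necessarily a lost observation. Women who stop after a week or more are asked for an exit mammogram (Protocol 7.2). The ITT population needs only one measure after baseline (SAP 6.1), and the primary analysis carries the last observation forward (SAP 6.9). Modest uptake restores 80% power, as shown above. This stands, and it makes the power figures lower bounds. It does not rescue the formula: exit attendance is voluntary, the documents give no uptake, and both the sample size and the interim rule count drop-outs as lost.

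Second, the harm needs high drop-out. The plan assumes 30%, the pilot saw about 25% stop for adverse events (Protocol 4), and Protocol 7.6 expects side effects mostly in the first three months, so late drop-out may be small. That is fair, but drop-out above plan is the only situation the rule is for.

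Some stronger readings are not supported:
- A reader might infer that the trial is short of power whenever the rule fires. At d = 40% it stays at or above 80% until about 2 further points are lost.
- A reader might infer that the look certainly rests on about 40 women. That needs the calendar reading. Month 3 is also a per-woman visit in Protocol 7.1.5, and on that reading the point lapses.
- A reader might put a low d into the formula and infer that the trial could be cut below 1,440. The text provides only for an increase.
- The words about power at best might be read as admitting that three-month drop-out is a lower bound. That is inference.

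**Conclusion.** The rule is wrong as written: it uses three-month drop-out to secure a number needed at six months, in both documents. By the plan's formula the shortfall at d = 40% is small for small late drop-out (77.7% power at 5 further points) and reaches 73.4% at 10. These figures assume that every drop-out is lost and that the trigger is near 40%, a value worked back from the stated 73% power. The absent trigger value may be a gap in the public text, and the mismatch of times does not depend on it. Whether three months means calendar time or each woman's follow-up is left open, and only the calendar reading leads to a look at about 40 Lund women. The correction is worth making because it is cheap and the rule cannot otherwise do its job, but this is a matter of power and not of validity.

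**What to change.** In Protocol 10.6.7 and SAP 6.8:

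1. Define d as projected pooled drop-out at six months: the Kaplan-Meier estimate at month 3 of each woman's follow-up, plus an allowance for months 3 to 6 stated beforehand. Update the allowance with blinded pooled data from the Lund women, who reach month 6 in May 2017.
2. Use this d in both the trigger and the formula, and make sure that the trigger value is printed.
3. State that three months means each woman's month 3. Hold the look when a fixed number, for example about 200, have reached it, early enough to extend enrolment.

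**Costs.** No unblinding, no by-arm data and no type I error cost, but a protocol amendment is needed. More women are requested when the rule fires: 1008/0.55 = 1,833 instead of 1,680 at 40% plus 5 points. More tablets may be needed too, since each dose is made in one batch (Protocol 7.11.2). The look may come later. With Stockholm opening in February 2017 (Protocol 5.4), 200 women cannot reach month 3 before May, and six-month treatment ending in December 2017 puts the end of enrolment near June. The longer timetable in 11.1 leaves more room. The allowance will rest on thin evidence: the documents give no drop-out timing for the 42-woman pilot, and 5 points among 40 Lund women is two women (0.05 x 40). It should therefore be stated openly as an assumption, with a range.
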